### **Secondary Mechanistic Outcomes**

Previous research has found a 40% prevalence of multi-drug resistant *E. coli* in faecal samples of UK nursing home residents (3) and a 37% prevalence of oral candida in hospitalised elderly patients (48). A meta-analysis of 6 trials of probiotics in critically ill patients reported probiotics reduced colonisation with multi-drug resistant gram negatives (OR 0.39 (95% CI: 0.16 to 0.95) (13). Despite high prevalence of AMR colonisation in CHR few studies have measured the effect of probiotics on this outcome. Hatakka et al (2006) found probiotics reduced the risk of oral candida in 276 older people by 75% (OR = 0.25, 95%CI 0.10- 0.65) (49). Stool and saliva samples at 6 to 12 months will provide 90% power at the 5% level to detect a 19% absolute reduction antimicrobial resistant bacteria and oral candida, assuming a 30% drop-out rate.

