The participant or consultee will be allowed as much time as they need to consider the information, and the opportunity to ask questions. Written Informed Consent (or exceptions as listed below) or Consultee Declaration will then be obtained by means of participant or consultee dated signature, respectively, and dated signature of the person who presented and obtained the Informed Consent/Consultee Declaration. The consent/declaration process will be undertaken by a suitably qualified and experienced delegated individual who has been authorised to do so by the Chief/Principal Investigator (e.g. care home staff/nursing staff/RN). A copy of the signed Informed Consent or Declaration Form will be given to the participant or consultee, respectively. The original signed form will be retained at the trial site.

Eligible CHR may participate in the trial even if they (or their consultee) prefer to opt out of the participant providing blood and/or stool and/or saliva samples.

Specific consent will be sought at trial entry from CHR with capacity to remain in the trial should capacity be lost during the trial.

**CHR lacking capacity:** Where a CHR lacks capacity to provide consent for themselves, a legal representative/guardian will be consulted who acts as their 'consultee'. The consultee may be a friend or unpaid carer or relative, an attorney acting under a lasting power of attorney, or a court appointed deputy who has a relationship or personal knowledge of the person who lacks capacity. The consultee will be provided with information about the trial and they will be asked their advice regarding the inclusion of the person and what the person's views would have been regarding inclusion in the research if they had capacity to make the decision for themselves. In the event that a consultee who has an unpaid or non-professional role in caring for the person cannot be identified, or is not willing to act, a nominated consultee will be appointed and consulted prior to including the resident in the trial.

In the event that a consultee themselves loses capacity or dies during the trial period, an alternative representative will be contacted to act as consultee and a new consultee Declaration Form will be completed. If there is no one to represent the CHR in the trial, the CHR will be excluded or withdrawn depending on whether a CHR has already been recruited to the trial.

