### 15.2 Data collection/assessment

Eligible participants or their consultee will have an appointment arranged at which informed consent or a consultee declaration (see section 10.3) will be obtained. A second baseline appointment will be made, at which baseline samples will be taken, and baseline data recorded.

The follow-up schedule will depend on the length of time that a participant has been in the study.

Where possible, participants will have a baseline assessment, and three- and 12-month follow-ups (participants randomised pre-December 2017).

Due to time limitations, some participants may have a truncated follow-up and will receive either a baseline assessment and 3 month follow-up (those randomised in May 2018), or a baseline

assessment, 3 month follow-up and a second follow-up between 6-10 months post-randomisation (those randomised between December 2017 and April 2018).

The target window for the 3-month follow-up is -2/+4 weeks.

The target window for the 12-month follow-up is 11 months +/- 1 month.

Infection, antibiotic use, adverse events and study product use will also be recorded by the RN from care home notes at regular intervals using the weekly record forms for 12 months post randomisation or until 31/10/18, whichever is sooner.

A sub-set of patients who have been taking the study product for a minimum of two months and who have had an influenza vaccination after the two month period will have an appointment arranged to attend a third appointment about four weeks (28 days) after the influenza vaccine.

Influenza vaccinations will be administered via routine care. The date of administration will be recorded.

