# **17 Statistical considerations**

## **17.1 Randomisation**

Participants will be individually randomised in a 1:1 ratio using minimisation. In order to achieve a balance of probiotic and placebo allocations within care homes, the care home from which a participant is recruited and gender of participant will be used as a minimisation variable. A random element, set at 80%, will be used in order to maintain the integrity of the minimisation process. The participants, treating clinicians, trial statistician and research nurses will remain unaware of the group to which participants are allocated during the trial. Pack IDs will be assigned probiotic / placebo allocations using randomly permuted blocks, and this list will be uploaded into the online system. This process will be carried out by a statistician independent of the trial team.

For more details, please consult the PRINCESS randomisation protocol.

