## **17.2 Sample size**

### **Primary Outcome**

The original target for the PRINCESS trial was to randomise 330 participants from around 20 care homes in Wales and England. This would provide 90% power at the 5% level to demonstrate a 10% relative reduction in cumulative antibiotic administration days (CAAD) (assuming an average CAAD of 17.4 days and an absolute reduction in the probiotic arm to 15.6 days per resident-year). We consider that a 10% reduction is feasible and would be clinically important.

This sample size accounted for 30% of participants being lost to follow-up due to withdrawal or death during the study.

An interim assessment of primary outcome ascertainment revealed that the mean percentage of days for which there are valid antibiotic administration data (i.e. either no antibiotics administered, or the number of days antibiotics have been administered in a given week) is 77.4%, or 283 days out of a possible 365 on average. This percentage varies depending on the length of time participants have been in the study. However, it remains high for participants who have been in the study for over six-months, and does not take into account other data sources that might be used (e.g. hospital discharge summaries, medication administration records, etc.). This is likely to therefore reflect an underestimate of the availability of primary outcome data, but nevertheless is a more accurate reflection of the likely level of follow-up when compared to our original assumption.

Given slower than anticipated recruitment, and this new information regarding the trade-off between the number of participants required and average length of follow-up, we will aim to randomise between 258 and 270 participants. Assuming a mean number of days for which primary outcome data will be available (i.e. accounting for follow-up time and missing data) of approximately 250 days, this will provide at least 82% power to detect a 10% relative reduction in CAAD.

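### The 90% power stated for AMR bacteria and oral Candida belongs to the superseded target of 330; at the current target of 258 to 270 it is about 80% to 84%.

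*Protocol*

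**What the plan says.** Section 17.2 has two parts.

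Under Primary Outcome, it gives an original target of 330, with 90% power and a 30% allowance for withdrawal or death. After an interim look at data completeness and slow recruitment, it states that "we will aim to randomise between 258 and 270 participants", and it restates the primary power as at least 82%. The Synopsis and section 10.1 give the same range with an upper limit of 330.

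Under Secondary Mechanistic Outcomes, it takes a "40% prevalence of multi-drug resistant *E. coli* in faecal samples of UK nursing home residents" and "a 37% prevalence of oral candida in hospitalised elderly patients", and concludes: "Stool and saliva samples at 6 to 12 months will provide 90% power at the 5% level to detect a 19% absolute reduction" in both outcomes, "assuming a 30% drop-out rate". No number randomised is named in that sentence.

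Three other places bear on the point:

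- Section 15.2 gives participants randomised in May 2018 a baseline and a 3-month assessment only. Those randomised from December 2017 to April 2018 have a second follow-up at 6 to 10 months.
- Section 10.3 lets residents take part even if they or their consultee "prefer to opt out of the participant providing blood and/or stool and/or saliva samples".
- Appendix 1 (Background) reports 310 residents recruited.

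**The concern.** The two paragraphs stand under one heading, but only the first was recalculated when the target fell. The second appears to have been edited for the truncated follow-up, since it speaks of samples at 6 to 12 months, yet its power is still the 90% that goes with 330. A reader would conclude that cutting the target cost the mechanistic outcomes nothing.

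This matters for interpretation. Reduced gut colonisation with AMR bacteria is one of the mechanistic hypotheses in section 5, and section 18.1 plans a mediation analysis through antimicrobial resistance. A null result read against 90% power would be taken as firmer evidence of no 19-point effect than the planned size supports.

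**Working it through.** **Inputs**

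- Control prevalence: 40% (AMR) and 37% (Candida), section 17.2.
- Absolute reduction: 19 points, giving 40% vs 21% and 37% vs 18%.
- Level 5%. Sidedness is not stated and is taken as two-sided (checked below).
- Loss 30%, section 17.2.
- Allocation, section 17.1: "Participants will be individually randomised in a 1:1 ratio using minimisation".

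**Formula.** Evaluable n per arm = N × 0.70 / 2. With p̄ = (p1 + p2)/2,

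SE0 = √[2p̄(1 − p̄)/n], SE1 = √[(p1(1 − p1) + p2(1 − p2))/n], power = Φ[(0.19 − 1.96·SE0)/SE1].

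**Reproducing the stated figure, N = 330** (n = 115.5 per arm)

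- AMR: SE0 = 0.0606, SE1 = 0.0593; (0.19 − 0.1188)/0.0593 = 1.20; power 88.5%.
- Candida: SE0 = 0.0588, SE1 = 0.0574; (0.19 − 0.1152)/0.0574 = 1.30; power 90.4%.

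Both lie within 2 points of 90%. Unpooled variance (89.4% and 91.1%) and the arcsine method (88.7% and 90.6%) agree. The stated 90% is the calculation for 330.

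**Power and detectable reduction by N, 30% loss**

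| N randomised | n per arm | AMR power | Candida power | Reduction detectable with 90% power, AMR / Candida |
|---|---|---|---|---|
| 330 | 115.5 | 88.5% | 90.4% | 19.4 / 18.9 points |
| 310 | 108.5 | 86.5% | 88.5% | 20.0 / 19.4 points |
| 270 | 94.5 | 81.5% | 83.8% | 21.3 / 20.6 points |
| 258 | 90.3 | 79.7% | 82.1% | 21.7 / 21.1 points |

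**Reverse check.** 90% power needs 122 per arm for AMR (244 in all) and 114 per arm for Candida (228). From 258 to 270 randomised, that allows a loss of only 5.4% to 9.6% for AMR (1 − 244/258; 1 − 244/270) and 11.6% to 15.6% for Candida (1 − 228/258; 1 − 228/270). The same sentence assumes 30%.

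**Sidedness.** The primary calculation settles this. A 10% reduction from 17.4 is 15.66. Two-sided, (1.960 + 1.282)² × (17.4 + 15.66)/1.74² ≈ 115 per arm, and 2 × 114.7/0.70 ≈ 328, against the stated 330. One-sided gives 267.

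**Second-visit samples (assumptions only; the protocol gives no count)**

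| Assumed loss | N = 258, AMR / Candida | N = 270, AMR / Candida |
|---|---|---|
| 30%, and a further 20% of the rest lack a sample | 70.3% / 73.0% | 72.2% / 74.9% |
| 30%, and a further 10% of the rest lack a sample | 75.3% / 77.9% | 77.3% / 79.8% |
| 30% in total | 79.7% / 82.1% | 81.5% / 83.8% |
| 22.6% in total (borrowed from the 77.4% valid antibiotic days) | 83.6% / 85.8% | 85.2% / 87.3% |

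The last row is an illustration: days with valid antibiotic data are not stool or saliva samples.

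**The case against.** The strongest reply is that 258 to 270 is not the whole design. The protocol keeps an upper limit of 330, and Appendix 1 reports 310 recruited. At 310 the shortfall against the original calculation is only about 2 points for each outcome. That narrows the gap and should be said. It does not rescue the sentence: section 17.2 rests its revised primary power on 258 to 270, and the mechanistic sentence cites neither 330 nor 310.

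A one-sided 5% test would give 87.6% to 90.5% at 258 to 270. No part of the protocol states one, and the primary calculation fits two-sided testing only.

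It can also be said that the outcomes are secondary, that the sentence sets no sample size or analysis, and that version 4.0 (15/04/2019) postdates the end of data recording on 31/10/2018. This is right, and it limits the severity.

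A reader might infer more: that power is lower still for the second-visit samples actually obtained, because May 2018 entrants have no second visit and samples may be declined. The documents do not support that as a finding. They give neither the number randomised in May 2018 nor the number of refusals. A second visit at 6 to 10 months leaves less time for drop-out, which works the other way. The sentence also does not say what its 30% covers; the link to withdrawal or death is made only for the primary outcome. With 310 recruited, power would fall to the 80% to 84% range only if about 40% had no second sample.

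**Conclusion.** The 90% is wrong as written for the current target. At 258 to 270 with 30% loss, power for a 19-point reduction is 79.7% to 81.5% (AMR) and 82.1% to 83.8% (Candida). At the 310 recruited it is 86.5% and 88.5%, and it is near 90% only at 330. These values rest on two-sided 5% testing, 1:1 allocation, and the protocol's own prevalences and loss.

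A reader might go further and say that the trial cannot deliver the stated power. That is too strong, since the upper limit of 330 is still permitted. Nor can the net effect of sample availability be signed: AMR power at 258 is about 75% if a further 10% lack samples and about 84% if total loss is 22.6%. The point is a minor to moderate correction to a secondary-outcome power statement. It affects neither the primary analysis nor the recruitment target.

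**What to change.** In section 17.2, Secondary Mechanistic Outcomes, do one of the following:

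- Name the number randomised and replace 90% by about 80% to 82% (AMR) and 82% to 84% (Candida) at 258 to 270, adding about 87% and 89% at the 310 recruited.
- Keep 90% and restate the detectable absolute reduction as about 21 to 22 points at 258 to 270, or about 19 to 20 points at 310.

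In either case, say that the test is two-sided and what the 30% loss covers. If second-visit sample availability is discussed, give it as a labelled assumption with a range on both sides of 30%, or use the actual sample counts if they are known.

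The cost is one or two sentences and a less favourable figure. No procedure, analysis or recruitment target changes.

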## **18 Analysis**

### **18.1 Main analysis**

The primary analysis will be by intention-to-treat, and will consist of a between-group comparison of the mean cumulative antibiotic administration days (CAAD) using Poisson regression. As the randomisation will be stratified by care home, the regression model will control for the care home a participant was recruited from. Negative binomial regression will be used in the presence of over-dispersed count data.

For secondary outcomes, depending on the type of data, a mixture of Poisson, linear, logistic and Cox models will be used to appropriately compare trial arms with respect to rates, means, proportions and time to events (see table below for more details).

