## 2 Synopsis

Short title	Probiotics to Reduce Infections iN CarE home reSidentS
Acronym	PRINCESS
Internal ref. no.	
Trial/study design	Two arm, individually randomised, double blind placebo controlled efficacy trial.
Trial/study participants	Care home residents in Wales and England
Planned sample size	Between 258 and 270 participants, with an upper limit of 330
Follow-up duration	
Follow-up schedule will depend on the length of time that a participant has been in the study.
 
Where possible, participants will have a baseline assessment, and three- and 12-month follow-ups.
 
Due to time limitations, some participants may have a truncated follow-up and will receive either a baseline assessment and 3 month follow-up, or a baseline assessment, 3 month follow-up and a second follow-up between 6-10 months post-randomisation.)
 
Infection, antibiotic use, adverse events and study product use is also recorded at regular intervals by the RN from care home notes for 12 months post randomisation or until 31/10/18, whichever is sooner.

Planned trial/study period	Once daily oral probiotics or placebo for 12 months or until 31/10/18, whichever is sooner

Primary objective	To evaluate the effect of a dose of daily oral probiotics on cumulative systemic antibiotic administration days (CAAD) for all-cause, acute infections
Secondary objectives	There are secondary objectives in infection, health utility, wellbeing, service use, mortality, antimicrobial resistance, oral and gut microbiology, immunology, blood and mechanisms (see section 5)
Primary endpoint	CAAD for all-cause infections over 12 months

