## 12 Intervention

Participants in the PRINCESS trial will be asked to take an oral dose of probiotic (*Lactobacillus rhamnosus*, LGG and *Bifidobacterium animalis* subsp. *lactis*, BB-12) or a matched placebo once daily for 12 months or until 31/10/18, whichever is sooner. The probiotic or placebo (referred to as Study Product) will be administered by the CHR's normal care giver and provided in capsule form. The preferred route of administration will be in the following order:

- 1) The capsule swallowed whole with water
- 2) The capsule emptied into a small amount of cold or lukewarm liquid and then swallowed
- 3) The capsule opened and its contents sprinkled onto cold or lukewarm food (not hot food) and then eaten

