### **Missing data assumptions and adjustments**

Given our proposed intensive monitoring schedule, missing data is likely to be minimal for participants who remain in the trial for the full duration. Where missing data is likely to occur, it will most likely be due to participant drop-out, with reasons for dropout falling into two broad categories, withdrawal from the trial and death.

Where responses are missing due to drop-out, these will be assumed to be missing at random given observed data, and appropriate modelling techniques will be used (e.g. likelihood-based methods or multiple imputation). Sensitivity analyses will be conducted using joint modelling approaches (e.g. selection and/or pattern mixture models) to explore departures from the missing at random assumption (51).

We will also explore stratifying deaths into two groups: death during an infection and death from any other cause. We will then investigate applying a missing at random-valid modelling approach to the deaths from any other cause and take a more extreme approach with those that died during an infection (e.g. assume that they would have remained on antibiotics for the remainder of the follow-up period).

Similarly, we will explore stratifying drop-out due to residents moving to another care facility into two groups: those who move for health-related reasons (e.g. from a residential home to a care home providing nursing care) and those who move for other reasons. A missing at random-valid modelling approach will be applied to the latter strata, with a more extreme approach taken for those dropping out due to moving from the care home for health-related reasons as this represents a decline in health, which may also be subject to unmeasured selection bias.

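### The primary model and the 12-month endpoint take no account of observed time, which varies by design and on which the 82% power rests

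*Protocol*

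**What the plan says.** - **Model.** Section 18.1 states that the primary analysis "will consist of a between-group comparison of the mean cumulative antibiotic administration days (CAAD) using Poisson regression", controlling for care home, with negative binomial regression if the counts are over-dispersed. The table in 18.2 repeats this. Neither place names an offset, an exposure term or person-time.
- **Endpoint.** The synopsis gives "CAAD for all-cause infections over 12 months".
- **Observation.** Section 15.2 has antibiotic use recorded "for 12 months post randomisation or until 31/10/18, whichever is sooner". Section 12 limits study product in the same way: "once daily for 12 months or until 31/10/18, whichever is sooner". The shortest schedule in 15.2 is "baseline assessment and 3 month follow-up (those randomised in May 2018").
- **Power.** Section 17.2 works in days per resident-year. It reports that the interim share of days with valid antibiotic data "is 77.4%, or 283 days out of a possible 365 on average". It then assumes about 250 days of available data per participant, allowing for both follow-up time and missing data.
- **Missing data.** Section 18.1 expects that "missing data is likely to be minimal for participants who remain in the trial for the full duration". It plans missing-at-random methods for drop-out, with harsher assumptions to be explored for deaths during an infection and for health-related moves. It does not mention truncation at the cut-off date or gaps in the weekly records.

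**The concern.** The calendar cut-off and the re-planned sample size turned this into a trial with unequal observed time, and section 17.2 was rewritten for that. The wording of the primary analysis and of the synopsis endpoint was not: it still describes a comparison of mean totals over a fixed period.

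An analyst who followed 18.1 literally would run an analysis that does not match the one powered. Spread in observed time would add variance that has nothing to do with treatment. Any difference between arms in observed time, through death, withdrawal or missed weeks, would enter the effect estimate. The reported means would also not be comparable with the planning figure of 17.4 days per resident-year.

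**Working it through.** **1. Length of observation.** From 1 May 2018 to 31 October 2018 is 183 days, and from 31 May it is 153 days. May 2018 entrants therefore have about 5 to 6 months, and early entrants have 12. For the interim figure, 0.774 × 365 = 282.5 days, which agrees with the stated 283.

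**2. Original sample size.** Inputs from 17.2: 17.4 days per resident-year, 10% reduction (15.66; the text rounds to 15.6), 90% power, 5% level (two-sided assumed), 30% loss.

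n per arm = (1.960 + 1.282)² × (17.4 + 15.66) / (17.4 − 15.66)² = 10.51 × 33.06 / 3.028 ≈ 115. The total is 230, and 230 / 0.7 = 329, which reproduces 330. The rounded 15.6 gives 309.

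**3. Revised power.** With t = 250/365 = 0.685 year and n per arm:

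Power = Φ( |λ1 − λ2| t / √[(λ1 + λ2) t / n] − 1.96 )

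| Total N | t = 0.685, rate 15.66 | t = 0.685, rate 15.6 | t = 1, rate 15.66 |
|---|---|---|---|
| 258 | 81.2% | 83.8% | 93.0% |
| 270 | 82.9% | 85.4% | 94.0% |

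For N = 258 with 15.66: 1.74 × 0.685 = 1.192; √(33.06 × 0.685 / 129) = 0.419; 1.192 / 0.419 − 1.96 = 0.88; Φ = 0.812. The stated figure of at least 82% is met to within a point or so when events are counted over observed person-time. A full 12 months of data on everyone would give 93%.

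**4. Bias if observed time differs by arm.** Without an offset or imputation, the expected ratio of means is the true rate ratio multiplied by the ratio of mean observed times. With no true effect, 1.00 × 0.95 = 0.95 and 1.00 × 0.90 = 0.90. A simulation (400 runs per setting, N = 258, Poisson model with robust standard errors) gave:

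| Observed time in probiotic arm | No offset: ratio, rejection | Offset: ratio, rejection |
|---|---|---|
| Equal | 1.00, 5% | 1.00, 6.5% |
| 5% less | 0.95, 16% | 1.00, 5% |
| 10% less | 0.90, 47% | 1.00, 6% |

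The 5% and 10% shortfalls are hypothetical; the protocol reports no data by arm.

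**5. Precision when observed time is balanced.** Assumed, not in the protocol: 70% of participants with 12 planned months, 30% spread uniformly over 5 to 11 months, and a valid-day share averaging 0.774. This gives a mean of 254 days and a coefficient of variation (CV) of 0.33. Expected counts are 17.4 × 254/365 = 12.11 and 15.66 × 254/365 = 10.90.

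- With offset: SE of the log ratio ≈ √[(1/12.11 + 1/10.90)/129] = 0.037
- Without offset: SE ≈ √[(1/12.11 + 1/10.90 + 2 × 0.33²)/129] = 0.055

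The target is |ln 0.9| = 0.105. Simulated power was about 82% with the offset and about 50% without it; the estimated ratio was 0.90 both ways.

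This is the pure Poisson case. In a second simulation with over-dispersed counts (dispersion about 8 and about 17, uniform recruitment over 17 months), the standard errors were 0.109 without and 0.102 with the offset, and 0.157 without and 0.152 with it. The offset thus reduced them by about 6% and 3%. The direction is stable; the size depends on the assumed spread and dispersion.

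**The case against.** **The offset may be in the SAP.** A protocol can fix the model family and leave the exposure term to the SAP, which was not among the documents reviewed. Nothing in 18.1 rules out person-time, and 17.2 thinks in those terms. This stands in part. But 18.1 and the synopsis word the target as a mean total over 12 months, and this does not match the quantity that was powered.

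**Truncation is already acknowledged.** The table in 5.1 asterisks the 12-month period, and its footnote explains the cut-off. This is true, but the footnote describes data collection. It does not say how unequal time enters the analysis.

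**Truncation should not bias the ratio.** It depends on entry date, and allocation is blinded and balanced within homes. This stands: bias needs observed time to differ by arm.

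Three stronger readings are tempting, and the protocol does not support them.

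- A reader might infer that unrecorded time is counted as free of antibiotics. Nothing says so. Section 17.2 treats a day as valid only when there is a record of no antibiotics or of the number of antibiotic days, so missing is kept apart from zero.
- A reader might infer that a resident who dies early looks like a success. Section 18.1 plans missing-at-random methods for drop-out. For deaths during an infection it explores assuming continued antibiotics to the end of follow-up, which goes the other way.
- A reader might set the expectation of minimal missing data against the 77.4% and call it a contradiction. The first is limited to participants who stay for the full duration. The second is not, and 17.2 says of it: "This is likely to therefore reflect an underestimate of the availability of primary outcome data". They are different quantities.

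**Conclusion.** The point holds as a mismatch within the protocol. The stated primary model and the synopsis endpoint do not account for the unequal observed time that the design creates and the power calculation assumes. The 82% is reproduced by a rate comparison over person-time, which 18.1 does not state.

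The consequences are conditional on raw totals being modelled without an offset or imputation. In that case balanced truncation lowers both means and costs precision, by an amount that depends on the assumptions in the working. Unequal observed time would bias the ratio in direct proportion, and the 0.95 and 0.90 are illustrations of this, not predictions. Separately, the missing-data section has no rule for calendar truncation or for gaps in weekly records. This should be corrected, but it does not show that the trial's result would be biased.

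**What to change.** - In 18.1 and the count rows of 18.2, include log(days with valid antibiotic data) as an offset, so that the analysis compares rates as 17.2 does.
- Word the synopsis endpoint as CAAD over follow-up of up to 12 months, consistent with the footnote in 5.1.
- Extend the missing-data sensitivity analyses to missing weeks and truncated time. Keep the approaches already planned for deaths and health-related moves, because an offset alone does not remove bias from informative missingness.
- Leave the sentence on minimal missing data as it is; the 77.4% figure is not a substitute for it.

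The cost is wording only. Section 17.2 shows that valid days are already derived from the weekly records, and no new data are needed.
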